5.3.2.3. Prior and concomitant medications

Incomplete prior/concomitant medication dates will be imputed as follows:

- If the medication date is missing completely, then the medication date will be replaced by the start of study treatment.
- If the day of medication date is missing, but the month and year are equal to the start of study treatment, then the medication date will be replaced by the start of study treatment. For example, if the medication start date is --/JAN/2015, and study treatment start date is 15/JAN/2015, then the imputed medication start date will be 15/JAN/2015.
- If both the day and month of medication start date are missing but the start year is equal to the start of study treatment, then the medication date will be replaced by the start of study treatment. For example, if the medication start date is --/---/2014, and study treatment start date is 19/NOV/2014, then the imputed medication start date will be 19/NOV/2014.
- In all other cases the missing medication day or missing medication month will be replaced by 1.
- Incomplete stop date will be replaced by the last day of the month (if day is missing only), if not resulting in a date later than the date of participant 's death. In the latter case the date of death will be used to impute the incomplete stop date.
- In all other cases the incomplete medication stop date will not be imputed.

5.3.2.4. Exposure

No imputation will be done for first dose date. Date of last dose of study drug, if unknown or partially unknown, will be imputed as follows:

- If the last date of study drug is completely missing and there is no End of Treatment eCRF page and no death date, the participant should be considered to be ongoing and use the cut-off date for the analysis as the last dosing date
- If the last date of study drug is completely or partially missing and there is EITHER an End of Treatment eCRF page OR a death date available (within the cut-off date), then imputed last dose date is:
 - = 31DECYYYY, if only Year is available and Year < Year of min (EOT date, death date)
 - = Last day of the month, if both Year and Month are available and Year = Year of min (EOT date, death date) and Month < the month of min (EOT date, death date)
 - = min (EOT date, death date), for all other cases.

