3.4. Baseline Variables

3.4.1. Study drug, study treatment and baseline definitions

In this study, ‘**study drug**’ refers to sasanlimab or encorafenib or binimetinib for Sub-Study A, sasanlimab or axitinib or SEA-TGT for Sub-Study B, and ‘**study treatment**’ (or ‘**treatment group**’) refers to:

- Phase 1b Sub-Study A Dose Level 0: sasanlimab 300mg + encorafenib 300mg + binimetinib 45mg
- Phase 1b Sub-Study A Dose Level 1: sasanlimab 300mg + encorafenib 450mg + binimetinib 45mg
- Phase 1b Sub-Study A Dose Level -1: (sasanlimab 300mg + encorafenib 300mg + binimetinib 30mg
- Phase 2 Sub-Study A: To be determined from Phase 1b
- Phase 1b Sub-Study B: sasanlimab **CCI** + axitinib 5 mg BID
- Phase 1b Sub-Study B: sasanlimab **CCI** + axitinib 3 mg BID
- Phase 1b Sub-Study B: sasanlimab **CCI** + axitinib 5 mg BID + SEA- TGT DL0
- Phase 1b Sub-Study B: sasanlimab **CCI** + axitinib 5 mg BID + SEA- TGT DL1
- Phase 1b Sub-Study B: sasanlimab **CCI** + axitinib 5 mg BID + SEA- TGT DL-1

- Phase 1b Sub-Study B: sasanlimab **CCI** + axitinib 3 mg BID + SEA- TGT DL0
- Phase 1b Sub-Study B: sasanlimab **CCI** + axitinib 3 mg BID + SEA- TGT DL1
- Phase 1b Sub-Study B: sasanlimab **CCI** + axitinib 3 mg BID + SEA- TGT DL-1
- Phase 2 Sub-Study B: To be determined from Phase 1b

Phase 2 Sub-Study B participants will be assigned in the following 3 study arms:

- Arm B1: Participants who report (i) no prior advanced or metastatic therapy and (ii) locally assessed PD-L1 TPS \geq 50%
- Arm B2: Participants who report (i) no prior advanced or metastatic therapy and (ii) locally assessed PD-L1 TPS \geq 1% and TPS $<$ 50%
- Arm B2: Participants who report (i) prior advanced or metastatic therapy and (ii) locally assessed PD-L1 TPS \geq 1%

Start and end dates of study treatment:

The date/time of first dose of study treatment in a combination group is the earliest date/time of the first non-zero dose date/time for the study drugs in the combination.

The date/time of last dose of study treatment in a combination group is the latest date/time of the last non-zero dose date/time for the study drugs in the combination.

Definition of baseline:

Definition of baseline for efficacy and PRO analyses and for safety analyses

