5.2.7. Definition of on-treatment period

Safety endpoints will be summarized based on the on-treatment period unless otherwise specified.

On-treatment period is defined as the time from the first dose of study treatment through minimum (30 days + last dose of study treatment, start day of new anti-cancer drug therapy – 1 day).

Safety data collected outside the on-treatment period as described above will be listed and flagged in listings but not summarized.

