YYYY = Year of min [max(PD date + 1, last dose of study treatment + 1), end date of new anti-cancer therapy], AND

MMM = Month of min [max(PD date + 1 day, last dose of study treatment + 1 day), end date of new anti-cancer therapy]

THEN

imputed start date = min [max(PD date + 1 day, last dose of study treatment + 1 day), end date of new anti-cancer therapy];

ELSE IF

YYYY = Year of min [max(PD date + 1, last dose of study treatment + 1), end date of new anti-cancer therapy], AND

MMM > Month of min [max(PD date + 1 day, last dose of study treatment + 1 day), end date of new anti-cancer therapy]

THEN

imputed start date = 01 MMM YYYY;

ELSE IF

YYYY < Year of min [max(PD date + 1, last dose of study treatment + 1), end date of new anti-cancer therapy]

THEN

imputed start date = DAY (Last day of MMM) MMM YYYY;

ELSE IF

YYYY > Year of min [max(PD date + 1, last dose of study treatment + 1), end date of new anti-cancer therapy]

THEN

imputed start date = 01 MMM YYYY.

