6.5.3.2. Exposure to encorafenib

The dose level is calculated as actual dose administered (mg/day).

Intended duration of treatment with encorafenib (weeks) = (end date – date of first dose of encorafenib +1)/7,

where end date = date of last dose of **encorafenib**

Duration of exposure to encorafenib (weeks) =

(last dose date of **encorafenib** – first dose date of **encorafenib** + 1)/7

Cumulative dose is the sum of the actual doses of **encorafenib** received in the study.

Actual Dose Intensity (DI)

- Actual DI (mg/week) = [cumulative dose (mg)] / [intended duration of treatment (weeks)]

Relative Dose Intensity (RDI)

- RDI (%) = $100 \times [\text{cumulative dose}] / [\text{intended cumulative dose per week} \times \text{number of weeks from first dose of study drug to last dose of study drug}]$
= $100 \times [\text{cumulative dose}] / [7 \times d \times \text{duration of exposure to encorafenib (weeks)}]$

Where d= 300 mg or 450 mg

The summary of exposure to encorafenib will include:

- Duration of exposure to encorafenib (weeks)
- Cumulative Dose (mg)
- Actual DI (mg/week)
- RDI (%)

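### The last-dose imputation rule has no branch for a known month in an earlier calendar year, so it imputes a date that the record itself rules out

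*SAP*

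**What the plan says.** Section 5.3.2.4 of the SAP has a block that begins "If the last date of study drug is completely or partially missing and there is EITHER an End of Treatment eCRF page OR a death". Call the earlier of the EOT date and the death date the reference date. The block has three branches:

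1. Year only, earlier than the reference year: "31DECYYYY, if only Year is available and Year < Year of min (EOT date, death date").
2. Month and year known: "Last day of the month, if both Year and Month are available and Year = Year of min (EOT date, death date"), with the further condition that the month is earlier than the reference month.
3. Everything else: "min (EOT date, death date), for all other cases".

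Section 5.3.3.4, on the start of new anti-cancer therapy, handles the same kind of partial date differently. Where month and year are known and the year is earlier than the reference year, it gives "imputed start date = DAY (Last day of MMM) MMM YYYY".

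The last-dose date is used in:

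- **Exposure duration**, for example "last dose date of encorafenib – first dose date of encorafenib + 1)/7" for encorafenib (section 6.5.3.2). Sections 6.5.3.1 and 6.5.3.3 to 6.5.3.5 do the same for the other drugs.
- **The window for safety summaries**: "On-treatment period is defined as the time from the first dose of study treatment through minimum (30 days + last dose of study treatment", or the day before new anti-cancer drug therapy if that comes first (section 5.2.7).

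For a combination, section 3.4.1 states: "The date/time of last dose of study treatment in a combination group is the latest date/time of the last non-zero dose date/time".

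**The concern.** A last dose recorded with month and year, in a year before the reference year, fails branch 1 because the month is known. It fails branch 2 because the years differ. It falls to branch 3 and is set to the reference date, which lies in a later calendar year than the one recorded.

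A less complete record does better: with only the year known, branch 1 at least keeps the date inside the recorded year. An imputation rule should not move further from the record as the record becomes more informative.

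What is at stake is exposure duration, dose intensity and RDI for the affected drug and, under conditions set out below, which adverse events count as treatment-emergent.

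**Working it through.** The SAP states no figure on this point, so there is nothing to reproduce. All dates below are illustrative assumptions, not trial data.

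**Step 1. Apply the branches.** Last dose recorded as November 2020, EOT 20JAN2021, no death.

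- Branch 1: not met, because the month is known.
- Branch 2: not met, because 2020 is not equal to 2021.
- Branch 3: imputed date 20JAN2021.

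The true date lies between 01NOV2020 and 30NOV2020.

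- 20JAN2021 − 30NOV2020 = 51 days
- 20JAN2021 − 01NOV2020 = 80 days

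The imputed date is 51 to 80 days late. Had only 2020 been recorded, branch 1 would have given 31DEC2020, which is 20 days earlier than 20JAN2021.

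**Step 2. RDI.** Assume 24 weeks of full dosing ending 30NOV2020, with cumulative dose unchanged by the imputation. RDI is cumulative dose divided by planned dose over the exposure duration, so

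RDI = 24 / (24 + 51/7) = 24 / 31.29 = 0.767, about 77% instead of 100%.

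**Step 3. Other dates.** First dose assumed 01MAR2021. Exposure = (last dose − first dose + 1)/7. RDI is for full dosing to the end of the recorded month, with cumulative dose unchanged. The month-end column follows the earlier-year branch of section 5.3.3.4.

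| Recorded last dose | EOT | SAP rule | Month-end rule | Excess days | Exposure, weeks (SAP vs month-end) | RDI under SAP rule |
|---|---|---|---|---|---|---|
| Dec 2021 | 10JAN2022 | 10JAN2022 | 31DEC2021 | 10 | 45.14 vs 43.71 | 96.8% |
| Nov 2021 | 10JAN2022 | 10JAN2022 | 30NOV2021 | 41 | 45.14 vs 39.29 | 87.0% |
| Oct 2021 | 15FEB2022 | 15FEB2022 | 31OCT2021 | 107 | 50.29 vs 35.00 | 69.6% |
| 2021 only | 10JAN2022 | 31DEC2021 | 31DEC2021 | 0 | 43.71 vs 43.71 | 100% |
| Oct 2021 | 10DEC2021 | 31OCT2021 | 31OCT2021 | 0 | 35.00 vs 35.00 | 100% |

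The last row shows that the rule works within a calendar year. Taking all 12 months of 2021 against reference dates on days 1 to 28 of every month of 2022, the SAP rule always returns the reference date, at least 1 day after the end of the recorded month.

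**Step 4. On-treatment window.** Take the second row, with no new anti-cancer drug therapy.

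- If the affected drug was the last one given, the window ends on 10JAN2022 + 30 = 09FEB2022 instead of 30NOV2021 + 30 = 30DEC2021, which is 41 days longer.
- If another drug in the combination has a complete last dose of, say, 05JAN2022, the study-treatment last dose moves only from 05JAN2022 to 10JAN2022, which is 5 days longer.
- If another drug was last given on 10JAN2022, the window does not move.

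**The case against.** The best case on the other side accepts the branch logic and disputes its reach. Most of it stands.

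- **TEAE window.** A reader might infer that every such date turns off-treatment events into treatment-emergent ones. The SAP does not support that. Section 3.4.1 takes the latest last dose across the combination's drugs, and every treatment group is a doublet or triplet. Section 5.2.7 also ends the window the day before new anti-cancer drug therapy.
- **RDI.** A reader might take the fall to 77% as certain. Section 6.5.3 defines cumulative dose for the oral drugs as a sum of actual doses. It does not say how that sum is formed when a dosing record has a partial end date. If the imputed end date also extends the dosing record, cumulative dose is overstated and RDI falls less or not at all. For sasanlimab, section 6.5.3.1 defines no RDI.
- **Efficacy.** A reader might infer that censoring is at risk in general. Section 5.3.3.4 uses the last dose only when the start date of new anti-cancer therapy is itself incomplete. Even then it enters through a maximum with the progression date and is bounded by the therapy's end date.
- **Frequency.** The SAP gives no rate of partial last-dose dates, so the number affected cannot be calculated. Section 5.3.1 has imputed values flagged in listings, so such records would be visible.

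A defence of deliberate conservatism does not stand. A cautious rule would not give an earlier date when less is known, and section 5.3.3.4 includes the branch that is missing here.

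**Conclusion.** The rule is wrong as written for one class of record: month and year known, year earlier than the reference year. Whenever it applies, the affected drug's last-dose date contradicts the record and its exposure duration is overstated. For encorafenib, binimetinib, axitinib and SEA-TGT, RDI is understated provided cumulative dose is unchanged.

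The size depends wholly on the dates: 10 to 107 days in the tabulated cases that cross a year end, and at least 51 days in the November 2020 illustration. Any lengthening of the on-treatment window is conditional, as described above.

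Only partial dates that cross a year end are affected, probably in few participants. DLT rate, durable response and objective response are not calculated from the last-dose date, so this is not a threat to the primary results. It is still worth correcting: the rule will be programmed literally, and the groups are small (Phase 1b cohorts of 3 to 6 or 3 to 4, and 20 per arm in Phase 2 of Sub-Study B).

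**What to change.** In section 5.3.2.4, change the condition of the second branch. Use the last day of the recorded month whenever month and year are both available and, taken together, precede the month and year of the earlier of the EOT date and the death date. This covers both an earlier month in the same year and any month in an earlier year, in line with section 5.3.3.4. Leave the year-only branch and the catch-all as they are; a date in the same month as the reference date still goes to the catch-all, which does not contradict the record.

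The cost is one line of SAP text and one programming condition. No clinical rule, endpoint or sample size changes.

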5.3.3. Imputation rules for date of last contact and efficacy assessments

5.3.3.1. Date of last contact

The date of last contact will be derived for participants not known to have died at the analysis cut-off using the latest complete date among the following:

- All participant assessment dates (blood draws (laboratory, PK), vital signs, performance status, ECG, tumor assessments)
- Start and end dates of anti-cancer therapies administered after study treatment discontinuation
- AE start and end dates
- Last date of contact collected on the ‘Survival Follow-up’ eCRF for ‘date last known alive’ (do not use date of survival follow-up assessment unless status is ‘alive’)
- Study drug start and end dates
- Randomization date
- Withdrawal of consent date
- Date of discontinuation on disposition eCRF pages (do not use if reason for discontinuation is lost to follow-up).

Only dates associated with actual examinations of the participant will be used in the derivation. Dates associated with a technical operation unrelated to participant status such as the date a blood sample was processed will not be used. Assessment dates after the cut-off date will not be applied to derive the last contact date.

5.3.3.2. Death date

Missing or partial death dates will be imputed based on the last contact date:

- If the date is missing it will be imputed as the day after the date of last contact
- If the day or both day and month is missing, death will be imputed to the maximum of the full (non-imputed) day after the date of last contact and the following:
 - Missing day: 1st day of the month and year of death
 - Missing day and month: January 1st of the year of death

5.3.3.3. Tumor assessments

All investigation dates (e.g., X-ray, CT scan) must be completed with day, month and year.

If there are multiple scan dates associated with an evaluation, i.e., radiological assessments occur over a series of days rather than the same day, the choice of date of assessment could impact the date of progression and/or date of response. If there are multiple scan dates associated with an evaluation, the earliest of the scan dates associated with the evaluation will be used as the date of assessment.

If one or more investigation dates for an evaluation are incomplete but other investigation dates are available, the incomplete date(s) are not considered for calculation of the assessment date and assessment date is calculated as the earliest of all investigation dates (e.g., X-ray, CT-scan).

If all measurement dates for an evaluation have no day recorded, the 1st of the month is used.

If the month is not completed, for any of the investigations for an evaluation, the respective assessment will be considered to be at the date which is exactly between the previous and the following assessment. If both a previous and following assessments are not available, this assessment will not be used for any calculations.

5.3.3.4. Date of start of new anti-cancer therapy

Incomplete dates for start date of new anti-cancer therapy (drug therapy, radiation, surgery) will be imputed as follows and will be used for determining censoring dates for efficacy analyses and in the derivation of the end of on-treatment period. PD date below refers to PD date by investigator assessment.

- The end date of new anti-cancer therapy will be included in the imputations for start date of new anti-cancer therapy. If the end date of new anti-cancer therapy is
 - completely missing then it will be ignored in the imputations below
 - partially missing with only year (YYYY) available then the imputations below will consider 31DECYYYY as the end date of the new anti-cancer therapy
 - partially missing with only month and year available then the imputations below will consider the last day of the month for MMMYYYY as the end date of the new anti-cancer therapy
- For participants who have not discontinued study treatment at the analysis cut-off date, last dose of study treatment is set to the analysis cut-off date in the imputations below.
- If the start date of new anti-cancer therapy is completely or partially missing, then the imputed start date of new anti-cancer therapy is derived as follows:
 - Start date of new anti-cancer therapy is completely missing
Imputed start date = min [max(PD date + 1, last dose of study treatment + 1), end date of new anti-cancer therapy]
 - Only year (YYYY) for start of anti-cancer therapy is available
IF YYYY < Year of min [max(PD date + 1, last dose of study treatment + 1), end date of new anti-cancer therapy] THEN imputed start date = 31DECYYYY;
ELSE IF YYYY = Year of min [max(PD date + 1, last dose of study treatment + 1), end date of new anti-cancer therapy]
THEN imputed start date = min [max(PD date + 1, last dose of study treatment + 1), end date of new anti-cancer therapy]

ELSE IF YYYY > Year of min [max(PD date + 1, last dose of study treatment + 1), end date of new anti-cancer therapy]

THEN imputed start date = 01JANYYYY

- Both Year (YYYY) and Month (MMM) for start of anti-cancer therapy are available

IF

YYYY = Year of min [max(PD date + 1, last dose of study treatment + 1), end date of new anti-cancer therapy], AND

MMM < Month of min [max(PD date + 1 day, last dose of study treatment + 1 day), end date of new anti-cancer therapy]

THEN

imputed start date = DAY (Last day of MMM) MMM YYYY;

ELSE IF

YYYY = Year of min [max(PD date + 1, last dose of study treatment + 1), end date of new anti-cancer therapy], AND

MMM = Month of min [max(PD date + 1 day, last dose of study treatment + 1 day), end date of new anti-cancer therapy]

THEN

imputed start date = min [max(PD date + 1 day, last dose of study treatment + 1 day), end date of new anti-cancer therapy];

ELSE IF

YYYY = Year of min [max(PD date + 1, last dose of study treatment + 1), end date of new anti-cancer therapy], AND

MMM > Month of min [max(PD date + 1 day, last dose of study treatment + 1 day), end date of new anti-cancer therapy]

THEN

imputed start date = 01 MMM YYYY;

ELSE IF

YYYY < Year of min [max(PD date + 1, last dose of study treatment + 1), end date of new anti-cancer therapy]

THEN

imputed start date = DAY (Last day of MMM) MMM YYYY;

ELSE IF

YYYY > Year of min [max(PD date + 1, last dose of study treatment + 1), end date of new anti-cancer therapy]

THEN

imputed start date = 01 MMM YYYY.

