5.2.5. Definition of start of new anti-cancer drug therapy

Start date of new anti-cancer drug therapy is used to determine the end of the on-treatment period (see Section 5.2.7).

The start date of new anti-cancer drug therapy is the earliest start date of anti-cancer drug therapy recorded in the 'Follow-up Cancer Therapy' or 'Concomitant Medication' eCRF pages that is after the first dose of study treatment. When start date of anti-cancer drug therapy is missing or partially missing, the imputation rules described in Section 5.3.3.4 should be applied using only data from the 'Follow-up Cancer Therapy' eCRF pages.

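### When PD is absent or not after last dose, an incomplete start date of new anti-cancer drug therapy can erase the 30-day post-dose safety window, and nothing stops that window ending before last dose

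*SAP*

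**What the plan says.** SAP 3.5.1 and 5.2.7 run the on-treatment period from first dose "through minimum (30 days + last dose of study treatment, start day of new anti-cancer drug therapy – 1 day". Safety data outside it are listed and flagged but do not enter the summaries. SAP 5.2.5 makes the link explicit: "Start date of new anti-cancer drug therapy is used to determine the end of the on-treatment period". The qualifying date there is the earliest one on the "Follow-up Cancer Therapy' or 'Concomitant Medication' eCRF pages that is after the first dose of study treatment". When that date is incomplete, 5.2.5 sends the reader to 5.3.3.4, using the follow-up therapy pages only.

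SAP 5.3.3.4 says its imputed dates "will be used for determining censoring dates for efficacy analyses and in the derivation of the end of on-treatment period". Its branches are:

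- **Completely missing:** "Imputed start date = min [max(PD date + 1, last dose of study treatment + 1), end date of new anti-cancer therapy". This quantity is called the reference date below. A completely missing therapy end date is ignored.
- **Year only:** the reference date if the year matches, 31 December if the recorded year is earlier, 1 January if it is later.
- **Month and year, month matches:** "imputed start date = min [max(PD date + 1 day, last dose of study treatment + 1 day), end date" of the new therapy.
- **Month and year, recorded month earlier:** "imputed start date = DAY (Last day of MMM) MMM YYYY".
- **Month and year, recorded month later:** the 1st of that month.

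**The concern.** One imputed date does two jobs. Whatever its merits for efficacy censoring, an early date shortens the safety window, because that window closes the day before it. If PD is absent or on or before last dose, the reference date is no later than last dose + 1, and the post-dose part of the window disappears. Toxicity, laboratory changes and ECG changes soon after stopping then leave the tables in SAP 6.6.1, 6.6.3, 6.6.5.1 and 6.6.6 because of an incomplete field on a follow-up page. SAP 5.3.2.2 leans the other way: a completely missing AE onset date is set to the start of study treatment, which keeps the event in.

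A second weakness is that 5.2.7 has no floor at last dose. 5.2.5 requires the new drug only to start after the first dose, so the period called on-treatment can close while study drug is still being given.

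**Working it through.** **Inputs.** LD = last dose of study treatment, PD = progression date, E = end date of the new therapy, S = its start date (recorded or imputed).

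- Reference date (5.3.3.4): R = min[max(PD + 1, LD + 1), E]. If E is missing it drops out. The SAP does not say what happens to the PD term when there is no PD; I assume it also drops out.
- Window end (5.2.7): W = min(LD + 30, S − 1).
- Post-dose days summarised = W − LD.

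**The plan's own figure.** With no new drug therapy, W = LD + 30, which gives the stated 30 days.

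**Varying PD and the recorded part.** LD = 10 June 2021, E missing. Entries are post-dose days summarised; a negative number means the window closes before last dose.

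| PD relative to LD | Missing | 2021 only | MAY | JUN | JUL | AUG |
|---|---|---|---|---|---|---|
| None, or on/before LD | 0 | 0 | −11 | 0 | 20 | 30 |
| +10 days | 10 | 10 | −11 | 10 | 20 | 30 |
| +20 days | 20 | 20 | −11 | 19 | 20 | 30 |
| +30 or +45 days | 30 | 30 | −11 | 19 | 30 | 30 |

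In the first row R = 11 June, so W = 10 June and W − LD = 0. A JUN start after last dose could truly lie anywhere from 11 to 30 June, a true window of 0 to 19 days; the rule gives the bottom of that range. With MAY recorded, S = 31 May and W = 30 May, 11 days before LD. With a missing start and E = 8 June, R = 8 June and W = 7 June, 3 days before LD.

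**Two cases with a known truth.**

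- LD 3 June, PD 1 June, start recorded as June, true start 28 June. R = 4 June, W = 3 June. The true window ends min(3 July, 27 June) = 27 June. Lost: 4 to 27 June, 24 days.
- LD 20 June, PD on or before LD, start recorded as July, true start 18 July. S = 1 July, W = 30 June. The true window ends min(20 July, 17 July) = 17 July. Lost: 1 to 17 July, 17 days.

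**A case in the other direction.** LD 1 June, PD 25 June, start completely missing, true start 10 June. S = 26 June, so W = min(1 July, 25 June) = 25 June. The true end is 9 June, so the window is 16 days too long.

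**Illustration under assumed inputs.** Suppose PD precedes last dose, every start is month-only, last dose is spread evenly over 2021, and the true start is uniform after last dose:

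| True start within | Share with 0 post-dose days | Mean window by rule | Mean true window |
|---|---|---|---|
| 30 days | 52% | 4.9 days | 14.5 days |
| 60 days | 26% | 14.9 days | 22.3 days |
| 90 days | 17% | 19.9 days | 24.8 days |

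These figures describe affected participants only. They say nothing about how many there are.

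**The case against.** The strongest reply is that the rule is not built to pick the earliest date. It takes the later of PD + 1 and last dose + 1, and it uses the last day of the month, or 31 December, when the recorded part is earlier than the reference date. A reader might infer from the zero-day case that the bias always runs towards fewer events. The 16-day overrun above shows that it does not; the direction depends on when PD occurred. A participant who stops for toxicity and progresses 30 or more days later keeps the full window even with a completely missing start.

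Safeguards also exist. Immune-related AEs, the events of special interest here, are captured to 90 days after last dose whatever the new therapy (Appendix 1) and have their own tables (6.6.4). Deaths within 30 days of last dose are tabulated without this cut-off (6.6.2). AEs and SAEs outside the window stay in the listings. Only drug therapy ends the window; radiation and surgery do not. The analyses use cleaned data (section 2), so few dates may stay incomplete.

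All of this stands and limits the reach of the point. It does not remove the zero-day window in the stated branches.

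It is also fair to say that the Concomitant Medication route concerns recorded dates rather than imputation, and that whether such drugs may be given during study treatment is for the protocol, which is not at hand. The missing floor is nonetheless a property of the derivation in the SAP.

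**Conclusion.** The point holds in a bounded form. With PD absent or on or before last dose, a completely missing, matching-year or matching-month start leaves 0 of 30 post-dose days in the summaries. A later recorded month can stop the window at the end of the month before. What is lost is non-immune-related TEAEs and SAEs, laboratory values and ECGs in the tables, not in the listings. With PD after last dose, part or all of the 30 days is kept. Separately, the window can close before last dose in three ways: a recorded month before that of last dose, a therapy end date before last dose, or an anti-cancer drug on the Concomitant Medication page that starts after first dose but during study treatment.

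A reader might try to turn this into a number of affected participants. The SAP gives no rate of incomplete dates. An assumed 10 to 20% of the 62 Phase 2 participants in Sub-Study A would be about 6 to 12, but that is only an upper limit under an assumption. A changed table also needs a new drug therapy, early or absent PD, an imputed date inside the 30 days and before the true start, and an event in the gap. The overall effect is therefore unknown. The case for acting is that the change is cheap and errs on the cautious side for safety.

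**What to change.** Restrict 5.3.3.4 to efficacy censoring and give the on-treatment period its own rule:

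1. Where the start of new anti-cancer drug therapy is partly known, impute the latest date consistent with the recorded parts, capped by the therapy end date.
2. Where it is completely missing, end the window at min(last dose + 30 days, known therapy end date − 1). Do not impute the start as last dose + 30: subtracting a day would close the window at day 29, and a known end date would be ignored.
3. In all cases set on-treatment end = max(last dose date, min(last dose + 30 days, new drug therapy start − 1)). For a completely missing start, the date from step 2 replaces the inner minimum.

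In the two worked cases the window would end on 29 June instead of the true 27 June, and on 20 July instead of the true 17 July: 2 and 3 days too long rather than 24 and 17 too short. The MAY row of the table would give 0 instead of −11.

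The cost is SAP wording in 3.5.1, 5.2.5, 5.2.7 and 5.3.3.4 and one derivation; efficacy censoring is untouched. The downside is that a few AEs that began after new therapy may count as treatment-emergent. In the case with PD on 25 June, the window would end on 1 July, 22 days past the true 9 June, against 16 under the present rule. Reporting how many participants have a window end that rests on an imputed date would show how much this matters.
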